Materials and methods

Participants

We examined whether the nicotine addiction related circuitries thus identified could be modulated by TMS and produce a reduction in nicotine addiction. We used a 20-TMS-session, sham-controlled, parallel-group, participant- and rater-blinded, randomized study design to test this hypothesis. The TMS cortical target that satisfied the pre-defined criteria in our pilot study was the dorsomedial prefrontal cortex (-15, 28, 48 in Talairach space. Details in Results). For this study, 30 SSD smokers (cigarettes per day ≥ 5 over the past 4 weeks) were enrolled.

Participants were randomly assigned to receive active or sham TMS at a 2:1 ratio, which allows for more statistical power in the TMS group to explore the association between changes of rsFC and changes of addiction severity. Of the 30 randomized, 26 completed, including 16 in the TMS and 10 in the sham group. The 2:1 ratio of randomization was chosen to assure more statistical power in the TMS group for exploring the association between changes of rsFC and changes of

nicotine addiction severity. Conditions including major medical and neurological illnesses, history of head injury with cognitive sequelae, mental retardation, substance dependence within the past 6 months or current substance abuse (except nicotine), and pregnancy were exclusionary. Subjects were asked not to consume caffeinated drinks prior to scan and be abstinent from alcohol for 24 hours prior to each fMRI and TMS session. No participant vaped or used electronic cigarettes before or during the treatment. Pregnant females were excluded. SSD smokers were not required to be smoking cessation treatment-seeking as the primary purpose here was to assess target engagement, i.e., whether TMS can impact the nicotine addiction severity-related circuitries and such effects, if found, would be related to change in nicotine addiction severity.

TMS

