Cigarettes per day and urine cotinine were the primary tobacco consumption indices and the FTND was used to represent severity of nicotine addiction. Previous factor analyses showed that the primary factor of the FTND was loaded with item 1, 3, and 5 of the six FTND questions, which asked time to first cigarette in the morning, whether the first cigarette in the morning or the rest of the cigarettes is most preferred, and whether one smokes more frequently in the first hour of the morning. These are symptoms representing severity of morning withdrawal symptoms or difficulty to maintain abstinence after overnight nonsmoking (Radzius et al., 2003). We used the sum of these items to refer to ‘morning smoking severity’ of the FTND. FTND score and cigarettes per day were obtained at baseline, session 5 (treatment week 1), 10 (week 2),

15 (week 3), and 20 (week 4). Imaging was performed at baseline, session 5, 10, and 20. The Brief Psychiatric Rating Scale (BPRS) measured the overall psychiatric symptoms(Hedlund et al., 1980). BPRS and urine cotinine were measured at baseline and session 20. All participants (whether receiving active or sham TMS) were encouraged to quit smoking using a standard psychoeducational clinical procedure. Staff conducting these procedures and assessments were blinded to group assignment.

Imaging data acquisition and analysis

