Resting-state fMRI scans were obtained using a 3T Siemens Prisma scanner equipped with a 64-channel head coil. The Human Connectome Project multi-band sequences were used: echo-planar pulse sequence with 2mm isotropic, TR=720ms, MB=8, AP/PA encoding, 4 runs \times 5.4 min each=24minutes). High-resolution (0.8 \times 0.8 \times 0.8mm³) T1-weighted MPRAGE images were acquired. Data were processed using Analysis of Functional NeuroImages (AFNI)(Cox, 1996) software. The preprocessed data were spatially smoothed to a FWHM of 6 mm. The linear trend, 6 motion parameters, their 6 temporal derivatives and time courses from the white matter and cerebral spinal fluid were removed as regressors of no interest. Time points with excessive motion (>0.3mm) and their neighboring time points were censored. Images were spatially normalized to the Talairach space(Talairach et al., 1988). Individual statistical maps were then calculated using a seed-based correlation analysis using dorsomedial prefrontal cortex as seed. The mean time-series within each seed ROI was correlated with the time course of each voxel in the brain to obtain resting-state functional connectivity (rsFC). Pearson's correlation coefficients were converted to z values using Fisher's r-to-z transform.

Statistical Analysis Plan

Demographics were compared using ANOVA or χ^2 tests. Target engagement was evaluated by extracting dorsomedial prefrontal cortex seeded rsFC with the extended amygdala regions, including bilateral hippocampus, amygdala, and substantia innominate. The linear mixed effect model was used to evaluate the group by time interaction of rsFC on FTND, cigarettes per day, and urine cotinine, although statistical significance using this full model was not expected as this was a proof-of-concept study. Exploratory analyses were conducted comparing TMS vs. sham at different time points using independent-sample t-test and comparing baseline vs. post-TMS measurements using paired-sample t-tests at $p < 0.05$. Effect sizes were calculated for nominally significant measures using Cohen's d . The primary analyses assessed the strength of the associations between changes of rsFC and changes in the smoking measures, using Spearman's correlation to account for non-normal distributions. All tests were two-tailed.

References

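### For the exploratory t-tests, Cohen's d is planned only where p<0.05, so the d values the plan produces are a selected set and on average too large in magnitude

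*Combined protocol and SAP*

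**What the plan says.** All the relevant rules are in the Statistical Analysis Plan section. After the mixed model it adds two families of t-tests. The first is between arms: "Exploratory analyses were conducted comparing TMS vs. sham at different time points using independent-sample t-test". The second is within participants: "comparing baseline vs. post-TMS measurements using paired-sample t-tests", at a nominal 0.05 level. All tests are two-tailed. The next sentence is "Effect sizes were calculated for nominally significant measures using" Cohen's d. Nothing in the documents says what estimate or interval accompanies a comparison that does not reach 0.05, or which SD standardises a paired d.

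The primary analyses are Spearman correlations between change in connectivity and change in the smoking measures. The Cohen's d sentence does not apply to them.

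The Participants section gives the numbers: "Of the 30 randomized, 26 completed, including 16 in the TMS and 10 in the sham group". Under the clinical assessments heading, FTND and cigarettes per day are taken at baseline and at sessions 5, 10, 15 and 20, and cotinine and BPRS at baseline and session 20. For scans, "Imaging was performed at baseline, session 5, 10, and 20".

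**The concern.** An estimate kept only when its test is significant has passed a filter on its own size. Those that pass lie further from zero, on average, than the quantity they estimate. The distortion is worst when power is low, and this plan does not expect much power: of the mixed model it says "although statistical significance using this full model was not expected as this was a proof-of-concept study".

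What is at stake is the reading of the exploratory effect sizes. In a study this small, a d calculated only for significant results will tend to look large whether the true effect is moderate or absent. Anyone who takes those values as estimates would be misled about magnitude.

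**Working it through.** The documents state no power, target effect or SD, so there is no figure to reproduce. The check works out what the filter does.

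**Inputs.** Two-sided 0.05 (Statistical Analysis Plan); 16 TMS and 10 sham completers (Participants). As an alternative, 20 v 10 is what an exact 2:1 split of the 30 randomised would give. The plan does not limit the t-tests to completers or state n by visit. True d is assumed over a range.

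**Smallest d that can qualify, equal-variance test, each contrast filtered separately.** Floor = t(0.975, n1+n2−2) × √(1/n1 + 1/n2).
- 16 v 10: 2.0639 × 0.4031 = 0.83.
- 20 v 10: 2.0484 × 0.3873 = 0.79.

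**Mean d among significant results, 16 v 10.** The estimate is 0.4031 × t, with t noncentral on 24 df and noncentrality d/0.4031, averaged over |t| > 2.0639. Without any filter, the mean estimate is 1.033 × true d, the ordinary small-sample bias. The selection factor is the signed mean among significant results divided by that unfiltered signed mean.

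| True d (assumed) | Chance of p<0.05 | Mean d, all results | Mean d, significant results | Selection factor |
|---|---|---|---|---|
| 0.3 | 0.11 | 0.31 | 0.99 | 3.2 |
| 0.5 | 0.22 | 0.52 | 1.09 | 2.1 |
| 0.8 | 0.48 | 0.83 | 1.19 | 1.44 |
| 1.0 | 0.66 | 1.03 | 1.27 | 1.23 |
| 1.5 | 0.95 | 1.55 | 1.60 | 1.03 |
| 2.0 | 0.997 | 2.07 | 2.07 | 1.00 |

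At true d=0 the two tails cancel, so the signed mean is zero. Only the magnitude is inflated: mean |d| is 1.015.

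**Welch test instead.** The floor is then only approximate. At true d=0.5 the mean |d| among significant results is 1.10 with equal SDs, 0.98 with the TMS-arm SD doubled and 1.29 with the sham-arm SD doubled.

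**Measure-level reading.** The word *measures* could mean that one significant visit releases d at all four post-baseline visits of that measure. There is then no floor. With the same true d at each visit and an assumed between-visit correlation of 0.5 to 0.9, the mean signed d released is about 0.62–0.84 at true 0.3, 0.76–0.95 at 0.5 and 0.94–1.08 at 0.8. Inflation is smaller but remains.

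**Paired tests, standardised by the SD of the change.** Floor = t(0.975, n−1)/√n.
- n=16: 0.53.
- n=10: 0.72, relevant only if paired tests are run in the sham arm.

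At n=16 the mean among significant results is 0.70, 0.77 and 0.92 at true values of 0.3, 0.5 and 0.8. That is about 2.3, 1.5 and 1.15 times the truth, with the small-sample bias included. Another standardiser would move these figures.

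**The case against.** The best reply is that the sentence says which effect sizes were calculated, not which results are shown. Means, SDs or t statistics with n would let a reader derive any missing d, and nothing in the plan forbids giving them. This stands as a limit on the claim: a reader might infer that the other comparisons are hidden or cannot be compared at all, and the documents do not support that. It does not remove the point, because the plan does not commit to giving those summaries either, and the d values it does produce are still chosen on p.

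A second reply is that the tests are labelled exploratory, the significance nominal and the study proof-of-concept. Those labels stand, and they keep the matter minor. They warn about false positives, though, and do not correct an estimate that is too large. Nor do the documents plan any reuse of these values, for example to size a later trial, so harm of that kind is only a possibility.

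A third reply is that the size of the bias is unknown, because no true effect is given. That is correct. Above zero, the direction is the same for every true effect tried, but the factor runs from about 3.2 down to 1.00. A reader might also set the mean |d| of 1.06 at true d=0.3 against 0.3 and quote a 3.5-fold inflation. That mixes absolute and signed values and includes the small-sample bias. Like for like, the factor is 3.2 signed, or 2.5 absolute (1.06 against an unfiltered mean |d| of 0.42).

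**Conclusion.** The point holds as a minor one, confined to the exploratory t-tests. Calculation of Cohen's d depends on p<0.05, and nothing elsewhere in the documents offsets that. If true effects are moderate (d of 0.5 to 0.8), selection alone inflates the between-arm values by roughly 2.1 to 1.44 times. This assumes 16 v 10, an equal-variance test and a filter on each contrast. Analysing 20 v 10 lowers the floor slightly, and the measure-level reading removes the floor and shrinks the inflation without abolishing it. For very large effects there is no material bias.

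A reader might infer that the trial's main result is distorted. It is not: the primary correlations lie outside this rule and no primary conclusion changes.

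**What to change.** Replace the Cohen's d sentence with:

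> For every exploratory comparison performed (TMS v sham at each assessed post-baseline visit, and every baseline v post-TMS comparison tested), Cohen's d with its 95% confidence interval is calculated and reported regardless of p-value and labelled exploratory; the standardiser used for paired comparisons is stated.

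This returns the mean between-arm estimate to within about 3% of the truth at 16 v 10 and settles whether the filter works by contrast or by measure.

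No new data are needed. The between-arm table would have 18 to 27 rows: FTND 4, cigarettes per day 4, cotinine 1, and connectivity at 3 visits for 3 bilateral or 6 unilateral regions (9 or 18). Testing morning smoking severity (4) and BPRS (1) as well makes it 23 to 32. Paired rows are extra. The intervals will be wide, for example −0.31 to 1.30 at an observed d of 0.5 with 16 v 10, which is a fair picture of what 26 completers can show.

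### The only analysis labelled primary, a correlation of change scores, cannot show whether TMS alters the circuit; the between-arm rsFC analysis is unclear, and Cohen's d is provided only for significant t-test results

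*Combined protocol and SAP*

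**What the plan says.** **Purpose.** Materials and methods, Participants, states that "the primary purpose here was to assess target engagement, i.e., whether TMS can impact the nicotine addiction severity-related circuitries", and then whether "such effects, if found, would be related to change in nicotine addiction severity". The second part is conditional on the first. The same section justifies the 2:1 allocation as one "which allows for more statistical power in the TMS group to explore the association between changes of rsFC and changes of addiction severity", and reports: "Of the 30 randomized, 26 completed, including 16 in the TMS and 10 in the sham group".

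**Analyses.** The Statistical Analysis Plan contains, in order:

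- A target-engagement sentence: "Target engagement was evaluated by extracting dorsomedial prefrontal cortex seeded rsFC with the extended amygdala regions". It names the seed and the regions but no comparison.
- A linear mixed model, worded as the group-by-time interaction of rsFC acting on FTND, daily cigarettes and cotinine. It has no primary, secondary or exploratory label, and the plan adds that significance was not expected of it.
- Independent-sample t-tests of TMS against sham at several times and paired t-tests against baseline, all labelled exploratory and at the 0.05 level. No measures are named.
- Cohen's d, for measures that reach nominal significance.
- The one item labelled primary: "The primary analyses assessed the strength of the associations between changes of rsFC and changes in the smoking measures", by Spearman's method.

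**Data.** Clinical and smoking related assessments says "Imaging was performed at baseline, session 5, 10, and 20" and "BPRS and urine cotinine were measured at baseline and session 20". FTND and daily cigarettes were collected at baseline and sessions 5, 10, 15 and 20.

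**The concern.** Whether TMS alters the circuit is a causal question, and randomisation was there to answer it. The analysis called primary does not use the randomisation. Changes in rsFC and smoking can move together in people on whom TMS had no effect, and TMS can shift rsFC without any link to individual change in smoking. A reader who takes the primary result as the verdict on target engagement could therefore be misled in either direction.

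The analyses that could answer the question are present but not pinned down. If rsFC is a predictor in the mixed model, that model does not estimate the effect of TMS on rsFC. If the t-tests include rsFC, half of the primary purpose rests on a test labelled exploratory.

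The Cohen's d rule is a separate problem. A proof-of-concept study is valued mainly for its effect estimates, and providing d only where p is below 0.05 selects on the result. In arms this small the selection is severe.

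**Working it through.** The documents give no power calculation or assumed effect size, so there is no planned figure to reproduce. The inputs are 16 TMS and 10 sham completers (Participants; 16 + 10 = 26, as stated) and two-sided testing at 0.05 (Statistical Analysis Plan). All true effects below are assumptions chosen to show a range. Effects are in SDs of whatever measure the test analyses.

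**1. Smallest between-arm d that would be given.** A pooled-variance t-test has 16 + 10 − 2 = 24 df, with critical value 2.064.

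- Standard error of d, in SD units: √(1/16 + 1/10) = √0.1625 = 0.403.
- Threshold: 2.064 × 0.403 = 0.83.

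No |d| below 0.83 can be significant, so none would be given under the rule.

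**2. Mean |d| among those given** (simulation of the 16 v 10 t-test with normal data):

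| Assumed true d | Chance d is given | Mean given abs(d) | Given values below the truth |
|---|---|---|---|
| 0.3 | 11% | 1.06 | 0% |
| 0.5 | 22% | 1.10 | 0% |
| 0.8 | 48% | 1.19 | 0% |
| 1.0 | 66% | 1.27 | 23% |
| 1.2 | 82% | 1.38 | 37% |

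Up to a true d of 0.8 every value given exceeds the truth, because the threshold itself does. The inflation shrinks as the true effect grows.

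**3. Can the correlation answer the first aim?** Two cases, with change scores as the analysed measure:

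- *No TMS effect on rsFC, but changes in rsFC and smoking truly correlated.* At correlations of −0.2, −0.4 and −0.5, Spearman is significant in 11%, 30% and 46% of trials with n = 16 (TMS arm), or 15%, 49% and 70% with n = 26 (both arms). These are true associations, not false positives. A between-arm t-test on rsFC stays at 5%.
- *TMS shifts rsFC by 0.5, 0.8 or 1.0 SD, with no link to smoking.* Spearman stays at 5%. The between-arm t-test detects the shift in 22%, 48% and 66%.

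The correlation can thus be positive with no engagement, and null with real engagement. Both sample sizes are shown because the Statistical Analysis Plan does not restate the analysis set; the allocation rationale points to the TMS arm.

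**4. What a between-arm contrast can deliver.** The unadjusted 95% CI half-width is again 2.064 × 0.403 = 0.83 SD of the analysed measure. By the noncentral t distribution, 80% power needs a true d of about 1.18.

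**The case against.** The strongest reply is that the first aim is already covered. The target-engagement sentence names the concept, the seed and the regions; a group-by-time model naming rsFC follows at once, then TMS-versus-sham t-tests at several times. Taking these together as the engagement analysis is natural, and making the association primary fits an allocation chosen to serve it. This stands to the extent that a reader who concluded that the plan has no between-arm analysis of rsFC would go beyond the text. What remains is that the model's wording leaves the role of rsFC open, the t-tests name no measure, and neither is identified as the answer to half of the primary purpose.

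A reader might also infer that all the study's standardised effects are inflated. They are not. The Spearman coefficients are standardised effects too, and neither they nor the mixed-model estimates depend on a significance condition. The inflation belongs to Cohen's d from the t-tests.

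Nor do the documents show that non-significant results are withheld. They say where d was calculated and are silent on means, SDs and test statistics. The Results section they refer to is not included, so actual reporting cannot be seen.

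The same filter applies to the paired t-tests, and one might infer that it treats the arms differently because they differ in size. That requires those tests to be run separately in each arm. The wording may mean the active arm only, so no weight is placed on it.

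Finally, completion is already reported, so naming an engagement analysis now cannot make it prespecified. That is right, and it governs how the fix should be labelled.

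**Conclusion.** The concern holds in two limited parts.

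First, the sole analysis labelled primary addresses only the second part of the stated purpose and cannot settle the first in either direction. Between-arm analyses that may settle it are listed but not clearly specified for rsFC. This follows from the text and does not depend on the assumed effects.

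Second, the Cohen's d rule, followed as written, gives between-arm values that are never below 0.83 in size. Their mean is about 1.06, 1.10 and 1.19 for assumed true effects of 0.3, 0.5 and 0.8. These figures assume normal data, equal variances and completers of 16 v 10; the threshold is the same whether levels or changes are compared.

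This should be fixed. It does not show that target engagement went untested or that the correlations are biased by selection.

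**What to change.** 1. Name the measures tested by t-test, rsFC among them, and calculate Cohen's d with a 95% CI for every one, whether or not significant.
2. Reword the mixed-model sentence so that rsFC, FTND, cigarettes per day and cotinine are each the outcome of their own group-by-time model (cotinine at baseline and session 20 only). Name the rsFC model, a single specification using baseline and sessions 5, 10 and 20, as the target-engagement analysis. Report its TMS-minus-sham estimates with 95% CIs as estimation, and label the designation post hoc.
3. Keep the Spearman correlation as the second step, described as association and not as evidence of engagement.

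The cost is some rewording and a few model fits on data already collected. The drawback is precision: with a half-width of about 0.83 SD unadjusted, and a d of about 1.18 needed for 80% power, the engagement contrast may well be null and should not then be read as showing no effect.
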